13.3. Disposition, Demographics and Baseline Characteristics

The number and percentage of patients in each population will be summarized. Patient disposition, including the number of patients screened, randomized, dosed, completing the IP, not completing the IP by reason for dropout, completing the MP, and not completing the MP by reason for dropout will be summarized for the ITT population. Patient demographics will be summarized for the ITT population and will include age, sex, race, ethnicity, height, weight, and body mass index.

Baseline characteristics will be summarized for the ITT population and will include age at UC symptom onset, age at UC diagnosis, years since UC symptom onset, years since UC diagnosis, prior anti-TNF use, corticosteroid use at Screening, concomitant UC medication use at Baseline, each component of the Mayo score, the Complete Mayo Score,

Compliance with randomized investigational drug will be summarized and will include the number of patients estimated to be < 80% compliant, 80 to 100% compliant, > 100%, and > 120% compliant.

13.4. Efficacy

13.4.1. Induction Period (Adult Patients)

Cohort 1 (double-blind RPC1063 1 mg once daily or placebo) will be used to formally assess the efficacy endpoints in the IP of the trial.

As Cohort 2 (open-label RPC1063 1 mg once daily) does not have a placebo control, no efficacy endpoints will be formally examined for the IP; however, the efficacy measures shown in [Section 6.2.1](#) will be summarized and described.

13.4.1.1. Induction Period Primary Efficacy Analysis (Adult Patients)

The primary analysis of proportion of patients in clinical remission (Three-component Mayo definition) at Week 10 will be carried out on the ITT population using a two-sided Cochran-Mantel-Haenszel (CMH) test at the 5% level of significance, stratified by corticosteroid use at screening (yes or no), and prior anti-TNF use (yes or no). Results will be expressed as number of patients in remission, remission percentages, weighted difference in remission percentages, odds ratio, and associated 95% confidence intervals (CIs) and p-values.

The primary analysis will be repeated on the PP population and on key subgroups of the ITT population including, but not limited to, patients with and without prior anti-TNF experience and patients with and without prior corticosteroid use. These will be considered sensitivity/supportive analyses only and will not be subject to family-wise Type I error control.

[REDACTED]

- [REDACTED]
- [REDACTED]
- [REDACTED]

13.4.1.2. Induction Period Secondary Efficacy Analysis (Adult Patients)

The 3 key secondary endpoints will be tested in order in a closed, hierarchical testing procedure in order to control the overall Type I error rate for multiple endpoints. If the primary endpoint is statistically significant, the proportion of patients with a clinical response (Three-component Mayo definition) at Week 10 will be tested at the 5% level of significance. If that endpoint is significant, then the proportion of patients with endoscopic improvement at Week 10 will be tested at the 5% level of significance. This testing procedure will continue through each of the 3 key secondary endpoints until an endpoint fails to reach statistical significance, after which all subsequent key secondary endpoints will be considered exploratory. Endpoints listed as other secondary endpoints (Section 6.2.2) will be tested in a nonhierarchical fashion without adjustments for multiplicity.

[REDACTED]

[REDACTED]

13.4.2. Maintenance Period (Adult Patients)

Patients with a clinical response [REDACTED] at Week 10 will be eligible to enter the MP. Patients who received RPC1063 1 mg and showed a clinical response during the IP (both Cohort 1 and Cohort 2) will be randomized in a double-blind manner to receive either RPC1063 1 mg or placebo in a 1:1 ratio. Patients randomized to placebo in Cohort 1 who demonstrate a clinical response during the IP will continue to receive placebo in the MP. Patients from either Cohort who do not show a clinical response may enter an optional Open-Label Extension trial, if appropriate.

MP endpoints are listed in [Section 6.2.4](#).

13.4.2.1. Maintenance Period Primary Efficacy Analysis

The primary analysis of proportion of patients in clinical remission (Three-component Mayo definition) at Week 42 (52 weeks total treatment) will be carried out on the ITT population using a two-sided CMH test at the 5% level of significance, stratified by clinical remission status at Week 10 of the IP (yes or no), and corticosteroid use at Week 10 of the IP (yes or no). Results will be expressed as number of patients in remission, remission percentages, weighted difference in remission percentages, odds ratio, and associated 95% CIs and p-values.

The primary analysis will be repeated on the PP population and on key subgroups of the ITT population including, but not limited to, patients with and without prior anti-TNF experience, patients with and without prior corticosteroid use, and patients with and without clinical remission at Week 10 of the IP. These will be considered sensitivity/supportive analyses only and will not be subject to family-wise Type I error control.

In addition to the primary analysis of MP clinical remission at Week 42 (52 weeks total treatment) using the Three-component Mayo definition described in [Section 6.2.1](#), the following alternative definitions of remission will be explored as sensitivity analyses:

- Rectal Bleeding Subscore ≤ 1 point and Stool Frequency Subscore ≤ 1 point and Endoscopy Subscore ≤ 1 point
- Rectal Bleeding Subscore = 0 points and change from Baseline in Stool Frequency Subscore ≤ 0 points (same or improved) and Endoscopy Subscore ≤ 1 point
- Partial Mayo Score of ≤ 2 points with none of the associated 3 subscores > 1 point

13.4.2.2. Maintenance Period Secondary Efficacy Analysis

The 6 key secondary endpoints ([Section 6.2.4](#)) will be tested in order in a closed, hierarchical testing procedure in order to control the overall Type I error rate for multiple endpoints. If the primary endpoint is statistically significant, the proportion of patients with a clinical response (Three-component Mayo definition) at 52 weeks will be tested at the 5% level of significance. If that endpoint is significant, then the proportion of patients with endoscopic improvement at 52 weeks will be tested at the 5% level of significance. This testing procedure will continue through each of the 6 key secondary endpoints until an endpoint fails to reach statistical significance, after which all subsequent key secondary endpoints will be considered exploratory. Endpoints listed as other secondary endpoints ([Section 6.2.4](#)) will be tested in a nonhierarchical fashion without adjustments for multiplicity.

[REDACTED]

[REDACTED]

13.4.2.4. Handling Missing Data

For proportion-based primary and key secondary efficacy endpoints, patients with missing Week 10 efficacy data for the IP and/or patients with missing Week 42 (52 weeks total treatment) efficacy data for MP will be considered non-responders using non-responder

imputation (NRI). Sensitivity analyses around missing data may include tipping-point analysis, missing data imputed using multiple imputation (MI) and analyzing observed cases with no imputation.

For continuous efficacy endpoints, missing data analysis may be performed using a multiple imputation (MI) method and observed cases with no imputation.

13.4.3. Safety Analyses

All safety analyses will be carried out on the Safety population.

Adverse events will be monitored during the trial and the data analyzed with respect to incidence within each treatment group as well as severity and potential relationship of the AEs to investigational drug. Adverse events with onset on, or after the first dose of investigational drug or with onset prior to the first dose of investigational drug that increase in severity on, or after the first dose of investigational drug will be considered treatment-emergent. Treatment-emergent AEs will be summarized for the Safety population by System Organ Class and Preferred Term, and presented in descending order of frequency within each System Organ Class. Serious AEs and AEs leading to discontinuation will be summarized similarly.

Associated laboratory parameters such as hepatic profile, renal function, and hematology values will be grouped and presented together. For each laboratory test, individual patient values outside the standard reference range will be flagged and listed. Shift tables will be produced showing the frequency of shifts from Baseline to the lowest and to the highest on-trial value in and out of the normal range as well as by visit. Changes from Baseline to each visit for each laboratory parameter will also be summarized.

The change from Baseline to each visit for each of the vital sign variables will be summarized. Abnormal vital sign values will be flagged and listed.

The change from Baseline to each visit for each of the ECG parameters will be summarized. An outlier analysis of ECG results will be conducted.

The change from Baseline for each of the PFT parameters will be summarized. An outlier analysis of PFT results will be conducted.

OCT parameters will be summarized.

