It is anticipated that approximately 400 adult patients treated with RPC1063 during the IP and who complete the IP (both Cohort 1 and Cohort 2) will be in clinical response at Week 10 and will be eligible to enter the randomized, double-blind, placebo-controlled MP. These adult patients in clinical response at Week 10 of the IP will be randomized to receive either RPC1063 1 mg or matching placebo in a 1:1 ratio. Adult patients in clinical response at Week 10 of the IP who were randomized to placebo (Cohort 1) will continue to receive placebo in the MP in a double-blind manner. Adult patients who have disease relapse at any time during the MP will be given the option to enroll in Open-Label Extension trial (RPC01-3102).

[REDACTED]

[REDACTED]

All patients will be evaluated for disease activity/efficacy at Week 42 of the MP (52 weeks of treatment).

[REDACTED]

Planned Number of Patients (approximately):

Induction Period: approximately 900 adult patients [REDACTED]

Cohort 1: approximately 600 adult patients (400 RPC1063 1 mg, 200 placebo)

Cohort 2: approximately 300 adult patients* (all receive RPC1063 1 mg)

*The number of patients in Cohort 2 may be increased if necessary to ensure approximately 400 patients who have received RPC1063 will be randomized in the MP.

[REDACTED]

Maintenance Period: Approximately 400 adult patients from IP Cohorts 1 and 2 who have received RPC1063

Patient Selection Criteria:

Inclusion Criteria:

Patients are eligible if they fulfill all of the following:

1. Must meet one of the following criteria:
 - Male or female adult patients aged 18 to 75 years (at Screening), inclusive for Cohort 1 or Cohort 2, or

[REDACTED]

[REDACTED]

2. Have had UC diagnosed at least 3 months prior to first investigational drug administration. The diagnosis should be confirmed by clinical and endoscopic evidence and corroborated by a

histopathology report (note: endoscopy and histopathology may be performed at Screening if no prior report is readily available)

3. Evidence of UC extending ≥ 15 cm from the anal verge as determined by Baseline endoscopy (flexible sigmoidoscopy or colonoscopy)
4. Have active UC defined as a complete Mayo score of 6 to 12 inclusive, with endoscopic subscore of ≥ 2 , a rectal bleeding score of ≥ 1 , and a stool frequency score ≥ 1
5. Must be currently receiving treatment with at least 1 of the following therapies and must continue on these therapies during Induction:

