The trial will include both patients that have received anti-TNF therapy and those who have not. The proportion of adult patients who have previously received anti-TNF therapy will be limited to approximately 30% in Cohort 1. The proportion of adult patients who have previously received anti-TNF therapy will be limited to approximately 50% in Cohort 2.

[REDACTED]

All patients will initiate investigational drug in accordance with a 7-day dose escalation regimen starting with RPC1063/ozanimod HCl 0.25 mg (equivalent to ozanimod 0.23 mg) or matching placebo (matching placebo for Cohort 1 [REDACTED] on Days 1 to 4 and RPC1063/ozanimod HCl 0.5 mg (equivalent to ozanimod 0.46 mg) once daily or matching placebo on Days 5 to 7. On Day 8, patients will receive the final dose RPC1063/ozanimod HCl 1 mg (equivalent to ozanimod 0.92 mg) once daily or matching placebo for 9 weeks.

The total duration of the IP is 10 weeks.

[REDACTED]

[REDACTED]

[REDACTED]

[REDACTED]

[REDACTED]

Maintenance Period:

It is anticipated that approximately 400 adult patients treated with RPC1063 during the IP and who complete the IP (both Cohort 1 and Cohort 2) will be in clinical response (by either definition in [Section 6.2.1](#)) at Week 10 and will be eligible to enter the randomized, double-blind, placebo-controlled MP. These adult patients in clinical response at Week 10 of the IP will be randomized to receive either RPC1063 1 mg or matching placebo in a 1:1 ratio. Adult patients in clinical response at Week 10 of the IP who were randomized to placebo (Cohort 1) will continue to receive placebo in the MP in a double-blind manner. Adult patients from Cohort 1 or Cohort 2 who do not show a clinical response at Week 10 or who lose response at any time during the MP may enter the optional Open-Label Extension trial, if appropriate.

[figure not shown]
Adult patients randomized in the MP will be stratified by clinical remission status (by either definition in [Section 6.2.1](#)) at Week 10 (yes or no) and corticosteroids use at Week 10 (yes or

no). Adult patients will be evaluated for disease activity/efficacy at Week 42 of the MP (52 weeks total treatment).

Trial schematics for Cohort 1 and Cohort 2 are presented in Figure 1

Figure 1: Trial Schematic for Cohort 1 and Cohort 2

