- ^l At Screening, a flexible sigmoidoscopy may be used if a colonoscopy is not required. A colonoscopy will be required if the patient has had left-sided colitis of > 12 years duration or total/extensive colitis of > 8 years duration and has not had a colonoscopy within 2 years (unless otherwise recommended by local and national guidelines) of the screening date to rule out dysplasia, or if the patient's age is > 45 years and the patient has not had a colonoscopy within 5 years to screen for polyps. The screening endoscopy must be completed no more than 21 days prior to randomization. A flexible rectosigmoidoscopy will be performed at Week 5 or later for adolescent patients who meet clinical symptom criteria for early discontinuation, with the understanding that the procedure may occur within approximately 7 days from the last visit prior to entering the OLE, to allow for preparation. The final decision to discontinue the patient early for entry into the OLE will be left to the discretion of the Investigator based on the Partial Mayo score and the endoscopy score.
- ^m Sigmoidoscopy should be performed no more than 10 days prior to the I 3 visit date in Induction and no more than 10 days prior to the M 5 visit date in Maintenance.
- ⁿ At Screening, patients will be issued with a Mayo diary and will be trained in the completion of the diary.
- ^o The Mayo partial clinical score on Visit I 1 should be combined with the central endoscopic read in order to assess the patient for "Mayo Score" entrance criteria.
- ^p DLCO, if locally available, will be done at Screening, Visit I 3, Visit M 3, and M 5/Early Term visit.
- ^q Early Term procedures performed at the Relapse Visit do not need to be repeated for patients who are early terminating due to relapse.

- ^r In cases when a patient's End of Treatment (Week 42 of Maintenance) visit and the first visit of the open-label extension study do not occur on the same day, an extra bottle of investigational drug may be dispensed to cover the period of time prior to entering the open-label extension.
- ^s The Safety follow-up visit should occur between 30 days to 60 days and at 90 days (± 10 days) after the last dose of investigational drug in the RPC01-3101 trial. However, if the patient continues treatment in the open-label extension, the safety follow-up visits are not required for the RPC01-3101 trial.

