8.4. Trial Discontinuation

Patients may voluntarily withdraw from the trial at any time. The Investigator will provide a written explanation in the source documentation to be entered on the appropriate eCRF page describing the reason for discontinuation.

The criteria for enrollment are to be followed explicitly. If a patient who does not meet enrollment criteria is inadvertently enrolled, the Medical Monitor must be contacted, and that patient will be withdrawn from the trial if continuation is determined to be a safety risk.

Reasons for discontinuation include, but are not limited, to the following:

- Physician decision: The Investigator must discontinue investigational drug if it is determined that it is not safe or in the patient's best interest to receive further treatment. The Medical Monitor should be promptly notified of the decision.

- Non-compliance with investigational drug: After consultation between the Investigator, the Medical Monitor, and the Sponsor when appropriate, a patient may be discontinued from the trial for failure to comply with dosing regimen as specified by the protocol.
- Non-compliance with protocol/protocol deviation: A patient fails to follow protocol procedures, or other event or decision that stands in contrast to the guidelines set in the protocol.
- Adverse event: A patient must be discontinued from investigational drug if, in the judgment of the Investigator or if specified in the protocol, the patient develops an AE such as an intercurrent illness or complication that justifies discontinuation of investigational drug.
- Lack of efficacy: Decision by the patient and/or the Investigator to discontinue investigational drug due to a lack of expected or desired effect related to a therapy.
- Withdrawal by Patient (or Patient's Parent/ Legal Guardian): The patient (or patient's parent/legal guardian) may choose to discontinue investigational drug at any time. Patients who discontinue investigational drug will be withdrawn from the study. Every effort should be made within the bounds of safety and patient (or patient's parent/legal guardian) choice to have each patient complete the Early Termination Visit and 30-day and 90-day Safety Follow-up Visits. If a patient (or patient's parent/legal guardian) withdraws consent/assent, the only additional investigational data to be collected will be the follow up of SAEs as mandated by the protocol.

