13.2. Statistical Methods

13.2.1. General Considerations

For the purposes of statistical analyses, the IP and the MP will be treated as two independent trials. The analysis of the IP will formally evaluate the efficacy and safety of RPC1063 1 mg vs. placebo as an induction therapy and the analysis of the MP will formally evaluate the efficacy and safety of RPC1063 1 mg vs. placebo as a maintenance therapy.

All efficacy and safety data will be listed by patient. Baseline for the IP is defined as the last observed measurement prior to the Day 1 receipt of investigational drug. Baseline for the MP is defined as the last observed measurement prior to the first dose of investigational drug following randomization into the MP. All safety and efficacy endpoints will be summarized by treatment group.

In general, descriptive summaries will be presented for the efficacy and safety variables collected. Continuous variables will be summarized using number of patients (n), mean, standard deviation (SD), minimum, median, and maximum. Categorical variables will be summarized using frequency counts and percentages.

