Ozanimod causes a dose-dependent reduction in peripheral lymphocyte count because of reversible retention of lymphocytes in lymphoid tissues. In the controlled RMS trials, mean absolute lymphocyte counts during treatment with ozanimod were approximately 45% of baseline values. Ozanimod may therefore increase the susceptibility to infections. In the Phase 3 RMS program, 0.4% of subjects on 0.46 mg ozanimod and 3.3% of subjects on 0.92 mg ozanimod developed ALC below $0.2 \times 10^9/L$ with no distinct pattern of timing. An association between ALC $< 0.2 \times 10^9/L$ and serious or opportunistic infections was not detected; however, an increased risk of infection cannot be ruled out.

In active-controlled completed RMS clinical trials, the overall rate of infections (35%) with Ozanimod was similar to that of IFN β -1a. Ozanimod treatment was associated with a higher frequency of viral upper respiratory tract infections, urinary tract infections, and herpes zoster. The overall rate of serious infections was similar between ozanimod (1%) and IFN β -1a (0.8%) in active-controlled MS clinical trials (also refer to protocol [Section 6.2.5](#)).

Phase 2 UC and CD data follow a similar pattern.

After discontinuing ozanimod 0.92 mg, the median time to recovery of peripheral blood lymphocytes to the normal range was 30 days, with approximately 90% of subjects recovering within 90 days.

Vaccinations

No clinical data are available on the efficacy and safety of vaccinations, including live attenuated, in subjects taking ozanimod. The use of live attenuated vaccines is to be avoided during treatment with ozanimod and for 90 days after treatment discontinuation.

Pulmonary Effects:

Pulmonary function is known to be affected by fingolimod, a non-selective S1P receptor modulator, and increased collagen or fibrin deposition in the lung as has been reported in toxicology studies with fingolimod. In nonclinical studies, ozanimod did not induce smooth muscle hypertrophy, and no effect on respiratory function was observed with ozanimod administration in rodents. In patients with multiple sclerosis, the pulmonary data indicate that mild reductions in FEV1 and DLCO occurred early in treatment with ozanimod 1 mg but were not clinically meaningful and did not progress. Pulmonary effects are not considered to be a risk associated with ozanimod treatment.

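### Maintenance adverse events: crude incidence by arm can be pulled in two opposite directions by early relapse exit and by residual drug effect in re-randomised placebo patients; add exposure-adjusted rates split at 90 days

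*Protocol*

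**What the plan says.** Protocol 13.4.3 is a single safety section for both periods. Adverse events are monitored and "the data analyzed with respect to incidence within each treatment group", then tabulated by system organ class and preferred term on the Safety population. It names no person-time denominator, time-to-event summary or time window. An event counts as treatment-emergent from the first dose of investigational drug, and the section does not restart that clock at Maintenance randomisation.

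The arms are meant to be compared. Protocol 13.2.1 says "the analysis of the MP will formally evaluate the efficacy and safety of RPC1063 1 mg vs. placebo as a maintenance therapy".

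Time in the Maintenance Period depends on outcome:
- Synopsis: "Adult patients who have disease relapse at any time during the MP will be given the option to enroll in Open-Label Extension trial".
- Section 7.1: patients "who lose response at any time during the MP may enter the optional Open-Label Extension trial".
- Section 8.4: "Patients who discontinue investigational drug will be withdrawn from the study".
- Table 1, footnote s: "if the patient continues treatment in the open-label extension, the safety follow-up visits are not required for the RPC01-3101 trial".

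The note to Figure 1 (section 7.1) restricts Maintenance randomisation to induction responders on RPC1063, so every re-randomised placebo patient has just had 10 weeks of active drug. Appendix 3 (Infections) says that after stopping 0.92 mg the "median time to recovery of peripheral blood lymphocytes to the normal range was 30 days", and that about 90% recover within 90 days.

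The supplied SAP covers induction only. Its section 2 assigns Maintenance analyses to a separate SAP. Its section 11.1 reports induction events as number and percentage of patients.

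**The concern.** A crude percentage per arm is a fair comparison when both arms are watched for similar lengths of time and the control arm is free of the test drug. In this randomised-withdrawal design neither condition is assured.

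First, if more placebo patients relapse and leave, the placebo arm has less time in which to record events, and a drug with no excess risk looks worse than it is. Second, early in the Maintenance Period the placebo arm still carries the drug's effect on lymphocytes, so a real excess of drug-related events looks smaller than it is. A single percentage per arm cannot separate the two.

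The stake is interpretation of infections and other events of special interest. SAP section 2 says the trial is intended as primary efficacy and safety evidence for marketing approval.

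**Working it through.** **1. The plan's own figure.** No number is stated for the safety comparison. The nearest is Maintenance power in Protocol 13.1: 16% vs 30% remission, 200 per arm, two-sided Fisher exact test, alpha 0.05, stated power 90%. Exact enumeration gives 0.900, so it is reproduced. These rates are the only documentary anchor for unequal outcome by arm: 84% vs 70% not in remission at 52 weeks.

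**2. Early exit alone, no true effect.** Let b be the 42-week event risk under full follow-up (assumed 5% and 30%) and e the proportion leaving by Week 42 (assumed). With constant hazards over T = 42 weeks, L = −ln(1−b)/T and H = −ln(1−e)/T:

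- crude incidence = L/(L+H) × [1 − (1−b)(1−e)]
- mean time on treatment = e/H

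Example, b = 5%, exit 40% placebo and 20% active: L = 0.00122, H = 0.01216 and 0.00531 per week. Placebo: 0.00122/0.01338 × (1 − 0.95 × 0.60) = 3.92%. Active: 0.00122/0.00653 × (1 − 0.95 × 0.80) = 4.49%. Ratio 1.14.

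| Assumed exit, placebo/active | Mean weeks, placebo/active | Crude ratio, b = 5% | b = 30% |
|---|---|---|---|
| 21% / 17.5% | 37.4 / 38.2 | 1.02 | 1.02 |
| 42% / 35% | 32.4 / 34.1 | 1.05 | 1.05 |
| 63% / 52.5% | 26.6 / 29.6 | 1.11 | 1.11 |
| 84% / 70% | 19.3 / 24.4 | 1.27 | 1.25 |
| 40% / 20% | 32.9 / 37.6 | 1.14 | 1.14 |
| 50% / 25% | 30.3 / 36.5 | 1.20 | 1.19 |
| 60% / 30% | 27.5 / 35.3 | 1.28 | 1.26 |

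The first four rows let 25%, 50%, 75% and 100% of the plan's non-remitters leave. The last three set placebo exit at twice active exit. The true ratio is 1.00 throughout, and events per person-time return it to 1.00.

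**3. Length of carry-over.** A Weibull curve through the two Appendix 3 points (50% recovered at 30 days, 90% at 90 days) has shape k = ln(ln 10/ln 2)/ln 3 = 1.09 and scale 30/(ln 2)^(1/k) = 42.0 days. The unrecovered fraction is S(t) = exp[−(t/42.0)^k]. Its area over 294 days is about 41 days, or 14% of the period (15% to 19% of placebo person-time with 20% to 60% exit). By window, the mean unrecovered fraction is 37.1/90 = 41% up to day 90 and 3.5/204 = 1.7% afterwards. Day 90 itself falls at 90/294 = 31% of the period.

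**4. Both together.** Assume a true hazard ratio of 2 and a 5% placebo risk. Active hazard is 2h; placebo hazard is h[1 + S(t)], that is, the drug effect fades as lymphocytes recover. Full follow-up without carry-over gives a risk ratio of (1 − 0.95²)/0.05 = 1.95 and a rate ratio of 2.00.

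| Situation | Measure | Active/placebo |
|---|---|---|
| Exit 20% in both arms, carry-over | crude | 1.70 |
| Exit 50% placebo / 20% active, no carry-over | crude | 2.42 |
| Exit 50% / 20%, carry-over | crude | 2.06 |
| Exit 50% / 20%, carry-over | exposure-adjusted, whole period | 1.70 |
| Exit 50% / 20%, carry-over | exposure-adjusted, first 90 days | 1.40 |
| Exit 50% / 20%, carry-over | exposure-adjusted, after 90 days | 1.96 |

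Exposure adjustment over the whole period removes the exit effect but not carry-over. The split brings the later window close to the true rate ratio.

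**The case against.** The strongest objection is that the governing document is missing. Maintenance analyses belong to a separate SAP, and person-year rates are often specified at that level. A reader might infer from 13.4.3 that Maintenance safety will rest on one crude percentage per arm. The documents do not show that: 13.4.3 is generic, and the percentage layout is explicit only in the induction SAP. What stands is that the Protocol names incidence as the measure and does not ask for more.

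A reader might also infer that the comparison is certainly and materially distorted. That is not supported either. Entry to the extension is optional, no exit rate by arm is given, and not being in remission is not the same as leaving. If exit merely follows the planned non-remission, with up to 75% of non-remitters leaving, the ratio is only 1.02 to 1.11.

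Carry-over can be overstated by treating 90 days as its length. That is an outer limit; the average under the fitted curve is about 41 days. The recovery figures concern lymphocyte counts, not events. Appendix 3 reports no detected association between very low counts and serious or opportunistic infections, though it does not rule out added risk. Lymphopenia itself is largely covered already, because 13.4.3 summarises laboratory values by visit and Maintenance visits fall at Weeks 8, 18, 30 and 42.

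Two further points are fair. Adverse event output is descriptive, with no hypothesis test, and the DSMB reviews safety by group about four times a year. And exposure adjustment alone can move the estimate away from the truth: in step 4 it gives 1.70, while the crude ratio of 2.06 benefits from offsetting errors. This is a reason to require the split, not to stay with the crude figure, since the offset depends on unknown exit rates.

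**Conclusion.** The point holds as a gap in the Protocol's stated measure, subject to what the Maintenance SAP contains. Crude incidence by arm can be distorted in two opposite directions. Unequal exit would give an apparent active/placebo ratio of about 1.02 to 1.28 with no true effect, over assumed exit of 21%/17.5% to 60%/30% (placebo/active) and constant hazards. These are scenarios, not bounds: a wider assumed gap of 60%/10% gives 1.44. Carry-over could reduce a true twofold hazard to a crude ratio of about 1.70 (against 1.95), if event risk tracks lymphocyte recovery and exit is 20% in both arms. It affects drug-related events only.

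More placebo exit is the probable direction, given planned remission of 16% vs 30%, but its size is not documented. The net direction is therefore unknown, and the documents do not support a claim that the plan favours or disfavours the drug. Efficacy results are not affected.

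**What to change.** In Protocol 13.4.3 and the Maintenance SAP, keep crude incidence and add the following for all AEs, SAEs and AEs of special interest:

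- exposure-adjusted incidence per 100 person-years (time to first event), counted from the first Maintenance dose;
- person-years per arm and the rate difference;
- the same figures overall and split at 90 days from Maintenance Day 1 for the two re-randomised arms, with patients who stay on placebo from induction shown separately.

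The text should also say that the Maintenance arms are those assigned at Maintenance Day 1. Read literally, the Safety population rule in 13.2.2 moves any placebo patient who has received RPC1063 to the RPC1063 group, which would take in every re-randomised placebo patient.

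If the Maintenance SAP already contains these tables, a cross-reference from 13.4.3 is enough. Otherwise the cost is one extra table layout from dates already collected, with no change to conduct or sample size. There are two limits to state beside the table: rates assume a constant hazard within each window, and the post-90-day comparison includes only patients who have not yet left, so it is no longer fully protected by randomisation.
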